15.3.1. Treatment Discontinuation

Treatment with study drug should be discontinued if any of the following occur:

- Development of accelerated hypertension (defined as systolic blood pressure \geq 180 *and* diastolic blood pressure \geq 100 mm Hg) that cannot be managed by the adjustment of concomitant medications such as antihypertensive medications.
- Development of congestive heart failure that cannot be managed by the adjustment of concomitant medications such as diuretics and antihypertensive medications.
- Development of diabetic signs/symptoms (ie, HbA1c $>$ 6.5%, or fasting plasma glucose $>$ 126 mg/dL, or classic symptoms of hyperglycemia with random plasma glucose $>$ 200 mg/dL).
- Subjects who undergo plasma exchange or IVIg due to lack of efficacy will be considered treatment failures and will be withdrawn from the study.
- Development of any other AE of at least moderate intensity and possibly, probably or definitely related to study drug that cannot be managed by the adjustment of concomitant medications.

15.4. Storage of Clinical Supplies

Acthar and placebo will be maintained in a temperature controlled, secure locked area with restricted access at the study site.

Study drug will be supplied in kits containing the appropriate amount of vials according to the treatment group to which the subject is assigned. Study drug will be stored under refrigeration between 2° to 8°C (36° to 46°F). Please refer to the Pharmacy Manual for complete information regarding storage and accountability of study drug.

15.5. Drug Accountability

In accordance with ICH requirements, the investigator will, at all times, be able to account for all study drug furnished to the study site. A drug accountability record will be maintained for

this purpose. The investigator must maintain accurate records indicating dates and quantity of study drug received, to whom it was dispensed (subject-by-subject accounting) and accounts of any study drug accidentally or deliberately destroyed. All unused study drug not involved in immediate subject dosing will be maintained under locked, temperature-controlled storage at the study site.

15.6. Compliance Monitoring

Prior to beginning the administration of study drug, subjects and/or their caregiver will be trained on dosing administration and must exhibit proper technique. Subjects and/or their caregiver will be trained on the completion of the study diary and will complete study diary entries to record all study drug administration and will bring it, along with all study drug kits (including used vials) to each visit. Each time study drug is dispensed compliance will be encouraged. Subject diary training is an ongoing process as the diary will be reviewed with the subject at each visit to monitor compliance with study drug administration.

16. EFFICACY ASSESSMENTS

Efficacy assessments will be evaluated at times specified in the Schedule of Study Events (Table 1). Below are general instructions for the administration of these assessments. Specific instructions and questionnaires will be provided in a separate document.

16.1. Subject Completed Assessments

The MSIS-29 is a subject reported outcome measure. When this assessment is required, it should be the first assessment done at any visit and must be completed prior to any study drug dosing. Subjects will be provided a quiet, private place to complete the assessment. Subjects will be instructed to answer all questions to the best of their ability and without help from others (including study staff, relatives, or friends). The study staff should review the questionnaire after it completed and encourage the subjects to complete any missing information. Subjects may refrain from answering any question. Study staff will record the refusal of subjects to answer any questions in the source documents.

16.1.1. MS Impact Scale (Version 1)

The MSIS-29 measures the physical (20 items) and psychological (9 items) impact of MS from the subjects perspective (Hobart et al, 2001). This validated questionnaire will result in a total score between 29 and 145 and can provide separate scores for physical and psychological impact. The MSIS-29 will be completed by the subject at all required times points during the study except on Study Day 14 when the MSIS-29 will be administered via telephone by a call center trained in the administration of the MSIS-29 or captured via a web portal.

16.2. Investigator (or Designee) and Blinded Rater Completed Assessments

The EDSS and FSS are to be completed by an appropriately trained blinded rater. The CGI-I assessment will be completed by an appropriately trained investigator or designee. When these assessments are required, they should be the done immediately after subject reported outcome/questionnaire completion (if applicable) and must be completed prior to any study drug dosing. The same trained rater should complete these assessments at all required time points for a subject.

16.2.1. Expanded Disability Status Score/Functional Systems Score

The EDSS is a 10 step assessment of neurological impairment/disability in MS ranging from 0 (normal neurological examination) to 10 (death due to MS) (Kurtzke, 1983) that is completed by a blinded rater.

The FSS is a component of the EDSS that requires the rater to score function in 7 functions (pyramidal, cerebellar, brainstem, sensory, bowel and bladder, visual, cerebral) on a scale from 0 (normal) to 5 or 6 (severe impairment) (Kurtzke, 1983).

Each site will designate 1 primary rater (neurologist or advanced practitioner experienced in performing EDSS/FSS) for each subject who will be responsible for performing all EDSS and FSS evaluations and who will be blinded to all other study aspects. The blinded rater should remain constant for each subject whenever possible. Subjects will be instructed not to discuss

MS therapy, any skin reactions, or other therapy side effects they have experienced with the blinded rater. The blinded rater will not be involved in any aspects of subject care and management other than performing the EDSS/FSS evaluations in subjects in the study.

16.3. Clinical Global Impression of Improvement

The CGI-I was developed for use in clinical research to provide a brief overview of the change in a subject's global function compared to baseline and regardless of study drug treatment (Guy, 1976; Busner and Targum, 2007). It requires a rating from 1 (very much improved) to 7 (very much worse).

17. SAFETY ASSESSMENTS AND PROCEDURES

The following safety assessments will be evaluated: AEs, physical examinations, clinical laboratory test results (chemistry, hematology, and urinalysis), vital signs, medical history, current medical condition, and weight. All safety assessments will be performed at times outlined in the Schedule of Study Events ([Table 1](#)[Table71](#)). Additional (unscheduled) safety assessments may be performed as needed.

17.1. Adverse Events

Adverse events will be recorded from signing of the ICF and followed by the investigator until the AE is resolved or stabilized. Any and all safety measures (which includes standard of care activities) should be provided by the study site to the subject. Any study site follow-up should be documented.

Refer to Section [20](#) for additional details on the handling of AEs and SAEs.

17.2. Medical and Surgical History

Medical and surgical history will be obtained at the Screening Visit. Medical history will include a review of the following systems: general, dermatological, respiratory, cardiovascular, gastrointestinal, genitourinary, gynecological, endocrine, musculoskeletal, hematological, neuropsychological, immune (allergies), and head, eyes, ears, nose, and throat. Historical and current medical conditions including date of last menstrual period for female subjects will be recorded.

17.3. Current Medical Conditions

At each visit after screening, subjects will be asked about any changes in medical conditions, specifically new medical conditions and worsening of existing medical conditions. Any changes since the Screening Visit will be recorded as AEs, as appropriate.

17.4. Physical Examination

A complete physical examination will be performed at the Baseline Visit and the Day 42/Early Termination Visit. The complete physical examination includes evaluation of the head, eyes, ears, nose, throat, neck (including thyroid), cardiovascular system (including assessment of heart, peripheral pulses, presence or absence of edema), lungs, abdomen (including liver and spleen, bowel sounds), lymph nodes, musculoskeletal system (including spine, joints, muscles) neurological system (including cranial nerves, reflexes, sensation, strength), skin, extremities and other conditions of note.

A limited physical examination, including evaluation of lungs, heart, abdomen, and extremities will be done at all other clinic visits.

The findings of the physical examinations will be recorded. Any change from the Screening Visit physical examination that is considered clinically significant by the investigator will be recorded as an AE.

17.5. Height and Weight

Height will be collected at screening only. Weight will be collected at specified times during the study.

17.6. Vital Signs

Vital signs will be obtained after the subject has been seated for 5 minutes (minimum) and will include systolic and diastolic blood pressures, pulse rate, respiratory rate, and body temperature. Additionally, at the Screening and Baseline Visits, blood pressure will be measured at least 3 times, with 5 minutes between assessments after the subject has been seated for a minimum of 5 minutes prior to the initial blood pressure assessment. The date and time for all vital sign assessments will be recorded.

The investigator may perform additional unscheduled vital sign measurements to evaluate or manage a suspected AE. These unscheduled vital sign measurements should be obtained after the subject has been seated for at least 5 minutes, if possible. Unscheduled vital signs will be recorded.

Screening/Baseline Assessments

A subject with systolic blood pressure > 140 mm Hg and diastolic blood pressure > 90 mm Hg (average of 3 assessments) at the Screening or Baseline Visits does not qualify for the study.

On Study Assessments

If an on study vital sign is not in the site's standard reference range, an AE will be recorded if the investigator determines the change is clinically significant or requires a change in the subject's clinical management.

17.7. Clinical Laboratory Tests (Chemistry, Hematology, Urinalysis, HbA1c, Hepatitis Serology, IGRA, and Pregnancy Tests)

The clinical laboratory tests are listed in [Section 31.1](#). All clinical laboratory tests will be done at a central laboratory facility except urine pregnancy (at the site) and IGRA (local laboratory). Specific instructions for collection, processing, storage, and shipment of clinical laboratory samples will be provided in a separate laboratory manual, where appropriate.

Samples for laboratory testing at all visits may be collected under fasted or nonfasted conditions. Fasting early morning samples are preferred, but a random daytime sample is acceptable. The date and time of the sample collection must be documented on the laboratory report. Investigators must review and sign laboratory reports. The clinical significance of each laboratory abnormality will be documented. New clinically significant laboratory abnormalities or clinically significant changes in laboratory values will be reported as AEs, as appropriate.

Hematology with differential, serum chemistry, and urinalysis samples will be collected at the specific times starting at screening and throughout the study.

In addition:

- All female subjects of child-bearing potential will have a serum pregnancy test at the Screening and Day 42/Early Termination Visits. Urine pregnancy tests will be

done at all other visits throughout the study. Results must be available prior to dosing with protocol mandated study drug. Subjects with positive results will be ineligible for study entry (Screening Visit or Predose) or withdrawn from the study if the positive result is obtained before the end of the treatment period. Any female subject that becomes pregnant before the end of the treatment period will be immediately withdrawn. All subjects who became pregnant after the last dose of the treatment will be continued in the study for follow-up visits. All pregnancies will be reported as per [Section 20.6](#).

If applicable, the subject's agreement to use contraception throughout their study participation (through the Follow-up Visit) will be documented.

- HBsAg and HBcAb will be performed at the Screening Visit. Results of these tests must be negative or nonreactive for subjects to qualify for the study.
- HCV will be performed at the Screening Visit. A positive HCV will automatically trigger a HCV PCR analysis. HCV PCR must be < 25 IU/mL to qualify for the study.
- IGRA for TB will be performed at the Screening Visit. Results of this test must be negative for subjects to qualify for the study.
- HbA1c will be performed at the Screening Visit. HbA1c must be $\leq 6.5\%$ for subjects to qualify for the study.

Out-of-Range Laboratory Values

Laboratory values from samples collected at the Screening Visit will be evaluated by the investigator for eligibility of the subject in the study. Clinical laboratory tests may be repeated once to determine subject eligibility.

Laboratory values that fall outside the reference range from samples collected during the study or at study exit or early termination will be assessed by the investigator for clinical significance. If the out of range value for samples is deemed clinically significant by the investigator, an AE will be recorded.

18. QUALITY OF LIFE/ HEALTH OUTCOME ASSESSMENTS

The following QOL/Health Outcome questionnaires are to be completed by the subject. When these assessments are required, they should be the second assessment done at any visit (after MSIS-29) and must be completed prior to any study drug dosing. Subjects will be provided a quiet, private place to complete the assessments. Subjects will be instructed to answer all questions to the best of their ability and without help from others (including study staff, relatives, or friends). The study staff should review the questionnaires after they are completed and encourage the subjects to complete any missing information. Subjects may refrain from answering any question. Study staff will record the refusal of subjects to answer any questions in the source documents.

18.1. [REDACTED]

[REDACTED]

18.2. [REDACTED]

[REDACTED]

19. STATISTICAL METHODS AND PLANNED ANALYSIS

19.1. General Considerations

This section provides a general description of the statistical methods to be used in analyzing both safety and efficacy data. The key statistical issues or considerations will be addressed. A more detailed statistical analysis plan will be provided in a separate document that will be finalized prior to database lock.

Summary statistics will be provided for all study variables with descriptive statistics (number of observations, mean, SD, median, minimum, and maximum) for numerical (or continuous) variables. Frequency and percentages will be calculated for categorical variables. Data summary and analyses will be performed with SAS 9.2 or higher.

19.2. Analysis Populations

- The Safety Population will include all randomized subjects who receive 1 or more doses of study drug.
- The Modified Intent-to-Treat (mITT) Population will include all enrolled subjects who receive 1 or more doses of study drug and who have at least 1 postbaseline EDSS score.
- The Per-Protocol Population will include the subset of the mITT population who complete the study as per protocol.

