19.5. Efficacy Analysis

A responder on EDSS is defined as a subject who achieves the following:

- ≥ 1.0 point improvement on EDSS score compared to baseline if baseline EDSS score was ≤ 5.5 .
- ≥ 0.5 point improvement on EDSS score if the baseline EDSS score was > 5.5 .

A responder on MSIS-29 is defined as a patient who achieves ≥ 8 point improvement on the physical subscale score of MSIS-29 compared to baseline.

Baseline is defined as the value observed prior to first dose of the study drug (Day 1).

The primary efficacy endpoint, the response rate on EDSS at Day 42, will be calculated by treatment group. Response rates and 90% Wilson CIs will be reported for each treatment group. These analyses will be performed for the mITT and Per-Protocol populations.

Summary statistics (n, mean, SD, median, minimum, and maximum) of the baseline value, the value at each scheduled postbaseline evaluation and the corresponding change from baseline for EDSS score will be presented by treatment group for all subjects in the mITT population and the Per-Protocol population.

A subject-by-subject data listing sorted by treatment group and subsequently by subject will be generated for all subjects in the mITT population.

For the secondary endpoints, the response rate endpoints will be analyzed and presented with the same approach as described above for the primary efficacy endpoint. The mean score endpoint will be calculated by treatment group. Mean, SD, and 90% CI will be presented by treatment group. All secondary efficacy analyses will use the mITT population.

For the exploratory endpoints, scores change from baseline will be calculated by treatment group. Mean, SD, and 90% CI will be presented by treatment group. All exploratory efficacy analyses will use the mITT population.

For all efficacy endpoints, the normality assumption of the data will be examined using appropriate normality test. If the test result shows the data is not normally distributed, then median, 10% and 90% percentiles will be presented instead of mean, SD and 90% CI.

The statistical analysis plan will describe in further detail the analyses for primary, secondary, and exploratory efficacy endpoints.

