19.9. Statistical Power and Sample Size Considerations

It is expected that 66 subjects will be randomized into 1 of 2 treatment groups: 80 U (1 mL) of Acthar per day for 14 consecutive days or placebo (1 mL) per day for 14 consecutive days in a 1:1 ratio (33 per group). The primary analysis is to generate point estimates and associated 90% CIs for the response rates on EDSS in the Acthar group and the placebo group at Day 42, respectively using a mITT analysis population. Assuming 3 subjects will not qualify for the mITT analysis population after randomization in each treatment group, there will be 30 mITT subjects in each group. Based on an expected 60% response rate in the Acthar group, the study can build a 90% Wilson CI of (45.1%, 73.3%) with approximate precision of 14.1%. Based on an expected 25% response rate in the placebo group, the study can build an approximate 90% Wilson CI of (15.7%, 41.5%) with approximate precision of 12.9%.

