19.10. Missing Data

Given the mITT design, an imputation or some other procedure for handling missing primary endpoints is required.

For the primary efficacy endpoint, subjects who do not provide data to allow classification as responders will be considered nonresponders, that is, missing data will be imputed as “nonresponder”. A similar approach will be applied to secondary efficacy endpoints that are proportions.

For continuous secondary efficacy endpoints collected directly from the CRF, the method of last observation carried forward (LOCF) will be used to impute the missing values. For other continuous secondary efficacy endpoints that need to be derived based on patients’ response to a questionnaire, if the responses to an entire questionnaire are missing, LOCF will be applied; otherwise, the method of handling missing response is described in each individual section for the secondary efficacy endpoint analysis.

A full description of missing data imputation method for all endpoints will be described in the statistical analysis plan.

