21. SUBJECT DISCONTINUATION OR WITHDRAWAL

21.1. Subject Withdrawal

Subjects who discontinue, or are withdrawn from the study for any reason, will be required to enter the follow-up period and have the Early Termination and Follow-up safety assessments (see [Section 14.5](#) and [Section 14.6](#)) to assess their continued well-being.

The reason for discontinuation will be recorded. A subject may be discontinued from the study for the following medical or administrative reasons:

Withdrawal by Subject

Subjects will be free to discontinue from the study at any time. Subjects who have received at least 1 dose of study drug but do not complete the study will not be replaced.

Lack of Efficacy

Subjects who undergo plasma exchange or receive IVIg following treatment with Acthar due to lack of efficacy will be considered treatment failures and will be withdrawn from the study.

Adverse Event

If a dosed subject suffers an AE that, in the judgment of the investigator, sponsor or MM, presents an unacceptable consequence or risk to the subject, the subject will be discontinued from further participation in the study.

Death

In the event that a subject dies during the study, death will be the reason for discontinuation.

Lost to Follow-up

Every effort should be used to maintain contact with subjects during their participation in the study. A subject may be considered lost to follow up if there is no response to 3 attempts to reach the subject by telephone and no response to a certified letter sent to the last known address of the subject. Efforts to contact the subject should be noted in source documentation.

Met Withdrawal Criteria

If a subject develops a condition that meets any of the exclusion criteria ([Section 12.2](#)) or fails to meet an inclusion criteria ([Section 12.1](#)) during the study that is not considered to be an AE or is noncompliant (eg, has a positive pregnancy during the screening or treatment periods or positive drug screening test), the subject will be discontinued from further participation in the study. Discontinuation is also mandated for safety and/or tolerability issues as outlined in [Section 15.3.1](#).

Other

If the above reasons are not applicable, please use the “Other” option and provide the appropriate reason for subject withdrawal.

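### The Per-Protocol set requires study completion, so subjects withdrawn as treatment failures after plasma exchange or IVIg leave its denominator for the primary endpoint

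*Combined protocol and SAP*

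**What the plan says.** Section 19.2 (and the Synopsis) defines the set by completion: "The Per-Protocol Population will include the subset of the mITT population who complete the study as per protocol". The mITT population has no such condition. It takes "all enrolled subjects who receive 1 or more doses of study drug and who have at least 1 postbaseline EDSS score".

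Section 19.5 gives response rates with 90% Wilson intervals for the primary endpoint and adds: "These analyses will be performed for the mITT and Per-Protocol populations". Section 19.9 places the primary analysis in mITT ("respectively using a mITT analysis population").

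On rescue for lack of efficacy, Section 15.3.1 says: "Subjects who undergo plasma exchange or IVIg due to lack of efficacy will be considered treatment failures and will be withdrawn from the study". Section 21.1 has a similar rule, worded for one arm: "Subjects who undergo plasma exchange or receive IVIg following treatment with Acthar due to lack of efficacy will be considered treatment failures". Section 21.1 also removes a subject whose adverse event "presents an unacceptable consequence or risk to the subject, the subject will be discontinued from further participation in the study".

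For missing primary outcomes, Section 19.10 says that "subjects who do not provide data to allow classification as responders will be considered nonresponders".

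**The concern.** Read together, these sections call a subject a treatment failure and then remove that subject from one of the two sets in which the primary endpoint is reported. The nonresponder rule in Section 19.10 does not repair this, because it acts only on subjects who are in the analysed set. No other section returns withdrawn failures to Per-Protocol.

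Membership of the set then depends partly on the outcome and not only on adherence. Section 9.1 says the pilot is meant to generate response rates for sizing a later, more definitive study. A Per-Protocol rate printed beside the mITT rate will be read as what happens when the protocol is followed. If failures have been dropped, part of any gap between the two rates comes from how the set was built.

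**Working it through.** **Inputs from Section 19.9.** 33 randomized per arm, less 3 who do not reach mITT, leaves 30 mITT subjects per arm. Expected response is 60% on Acthar and 25% on placebo.

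**Reproducing the plan's intervals.** The 90% Wilson interval has centre (p + z²/2n)/(1 + z²/n) and half-width z·√(p(1−p)/n + z²/4n²)/(1 + z²/n), with z = 1.645 and n = 30.

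- Acthar, 18/30 = 60.0%: 45.1% to 73.3%, half-width 14.1%. This matches the plan.
- Placebo, 8/30 = 26.7%: 15.7% to 41.5%, half-width 12.9%. This matches the plan. A literal 25% (7.5/30) would give 14.4% to 39.7%, so the printed interval rests on 8 whole responders. I use 8/30 below.

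**Effect of the completion condition.** Suppose k mITT subjects in an arm are withdrawn after plasma exchange or IVIg for lack of efficacy and are nonresponders in mITT. With x responders, the rate changes from x/30 to x/(30 − k), which is larger whenever k > 0. The documents give no value for k, so the values below are assumptions.

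| k removed per arm | Acthar | Placebo |
|---|---|---|
| 0 | 18/30 = 60.0% | 8/30 = 26.7% |
| 1 | 18/29 = 62.1% | 8/29 = 27.6% |
| 3 | 18/27 = 66.7% (90% CI 50.8 to 79.5) | 8/27 = 29.6% (90% CI 17.6 to 45.4) |

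At k = 3 the rise is 6.7 points on Acthar and 3.0 points on placebo, with no subject's outcome changed.

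**Contrast between arms.** With nobody removed the difference is 60.0 − 26.7 = 33.3 points. Removing three per arm gives 66.7 − 29.6 = 37.0 points (from unrounded rates). Removing none on Acthar and three on placebo gives 60.0 − 29.6 = 30.4 points. The direction depends on where the failures fall.

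**Other exclusions.** Section 14.6 collects EDSS at early termination, so a subject withdrawn for an adverse event may have improved. If three Acthar subjects are excluded and two of them are responders, the rate is 16/27 = 59.3%, slightly below 60.0%. The upward direction is therefore certain only for the lack-of-efficacy withdrawals.

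**The case against.** There is a fair case for leaving the definition alone.

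- **IVIg is prohibited.** Section 13.1 bars it through Day 42, and excluding recipients of a prohibited therapy from a per-protocol set is conventional. This stands as far as it goes: an IVIg recipient cannot be said simply to have followed the protocol. But plasma exchange is not named on that list, and when either therapy is given for lack of efficacy the plan itself records a treatment failure. Excluding such subjects still selects on outcome.
- **The analysis is supportive and descriptive.** Section 19.9 makes mITT primary, no hypothesis test depends on Per-Protocol, and Section 19.4.4 tabulates reasons for discontinuation. All of this stands, and it limits the consequence. The k = 3 rates also lie inside the planned mITT intervals.
- **Detail is deferred.** Section 19.1 promises a separate, more detailed SAP, which is not in the text reviewed. A later clarification cannot be ruled out, but the definition as written contains none.

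A reader might also infer more than the documents support:

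- **That all nonresponders leave the set.** They do not. A subject without an EDSS response who reaches Day 42 otherwise per protocol stays in the denominator.
- **That adverse-event withdrawals are failures too, so Per-Protocol must exceed mITT.** Withdrawal for an adverse event is a safety decision and does not establish nonresponse.
- **That the primary result, or the sizing of the later study, is biased.** mITT keeps the rescued subjects if they have a postbaseline EDSS, and nothing says the Per-Protocol rate will be used for sizing.

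**Conclusion.** The concern holds for one group: subjects withdrawn after plasma exchange or IVIg for lack of efficacy. As written, Per-Protocol drops them, and for them the effect on each arm's rate can only be upward. With 30 mITT subjects per arm the size runs from nothing at k = 0, through 2.1 points on Acthar and 0.9 on placebo at k = 1, to 6.7 and 3.0 points at k = 3. The contrast between arms may widen or narrow.

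This rests on three assumptions: the plan's expected response rates, values of k that the documents do not supply, and counting these subjects as nonresponders in mITT. The last follows from their failure label and Section 19.10, although no section says outright that a treatment failure is an EDSS nonresponder. The net difference between Per-Protocol and mITT also depends on who else is excluded. The primary mITT analysis is not affected, so this is a worthwhile correction to a secondary presentation of the primary endpoint, not a threat to the main result.

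**What to change.** In Section 19.2, the Synopsis and the SAP:

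1. Define Per-Protocol as mITT subjects without major protocol deviations, with the deviation criteria and each subject's classification settled before unblinding. Remove study completion as the criterion.
2. State that subjects withdrawn for lack of efficacy after plasma exchange or IVIg remain in Per-Protocol as Day 42 nonresponders, and that the rescue itself is not an excluding deviation.
3. Apply to adverse-event withdrawals the same dosing-compliance and deviation criteria as to everyone else. There is no need to count all of them as nonresponders.
4. Reconcile Section 21.1, which words the failure rule for subjects treated with Acthar, with Section 15.3.1, which does not limit it to one arm, so that it is clear to whom the counting rule applies.

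The cost is wording. No new data, visits or subjects are needed. The downside is slightly less favourable Per-Protocol rates if any such rescues occur.
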